## Study Description

### 1. STUDY PURPOSE AND RATIONALE

Patients with Rheumatoid Arthritis (RA) are at increased risk for developing heart failure (HF) compared to matched non-RA controls. In addition, HF is one of the main causes for premature death and a major contributor to the reduced - compared to the general population - lifespan of RA patients.

Preliminary data show that patients with RA have a lower LV mass than non-RA controls, and that this decrease in LV mass is associated with a lower cardiac output. Assuming that the decrease in the cardiac output could be indicative of pre-clinical HF, this is in contrast with what is observed in the non-RA patients, where the development of HF is preceded by an increase in LV mass. The reasons for a decreased LV mass in RA, and how this may be linked or lead to a compromised LV function are not known. Furthermore, based on preliminary data that associate the presence of specific RA characteristics (such as the presence of CCP antibodies) with a decrease in the LV mass, we can hypothesize that RA related inflammation within the myocardium may be causing myocardial cell death or apoptosis. In addition, based on data showing diffuse subendocardial hypoperfusion in patients with RA we can hypothesize that inflammation may affect the endothelium of the myocardial microvasculature, and interfere with myocardial perfusion leading to myocardial atrophy.

The first aim of this study is to evaluate and identify factors that are associated with the phenotype of low LV mass. We will enroll 150 RA patients in the study. Some of the potential low LV mass predictors to be studied include: RA associated characteristics (e.g., anti-CCP antibody titers), duration of articular disease, the degree of systemic and myocardial inflammation, and alterations in myocardial perfusion. LV structure and function will be assessed by cardiac PET-CT scan and 3-dimensional echocardiography (3D ECHO).

TNF inhibitors are an FDA approved class of medications indicated for the treatment of RA when initial treatment (usually with methotrexate) has failed to achieve remission of RA disease activity. TNF inhibitors are part of the standard of care management of RA. It is estimated that currently up to 20% of patients with RA are being treated with TNF inhibitors. More than 10 years of experience with these agents support the use of these agents for RA patients who do not respond to initial treatment. While TNF inhibitors have revolutionized the treatment of articular RA, their effects on heart failure (HF) has not been elucidated. Clinical trials in non-RA patients with advanced HF showed that these medications are not beneficial and may even be detrimental. Even though similar robust studies have never been performed in RA patients, product information sheets for all of the TNF inhibitors warn against their use in RA patients with advanced HF. However, their use is allowed for the treatment of RA in patients with moderate or mild HF with careful monitoring. Animal data, recent RA cohort data, and our preliminary data in RA patients suggest that TNF

inhibitors may prevent HF and/or improve LV function in RA. So far, no studies have investigated the direct effect of this class of drugs on myocardial function and structure. The hypothesis that TNF inhibitors may have a differential effect on the failing myocardium - depending on whether patients have RA or not - would reconcile the contradictory literature. Assuming that systemic or myocardial inflammation may be the primary force leading to HF in RA, we hypothesize that TNF inhibitors may be beneficial in preventing or improving HF in patients with RA. We will address this hypothesis first by examining the effect of TNF inhibitor treatment in RA patients without heart failure. If safe, further studies can direct attention to RA patients with heart failure.

The second aim of the study will target 50 of the 150 RA patients enrolled in aim 1, and will evaluate the effect of treatment with TNF inhibitors on left ventricular (LV) structure and function, and also myocardial inflammation and perfusion. In this aim we will investigate the effect on TNF inhibitor treatment directly on the myocardium in patients without HF, or other known cardiovascular disease. Thus we will not enroll any patients with HF, but only patients free of any cardiovascular disease. Participants in need of treatment to control their disease activity despite methotrexate will be randomized to receive treatment with either a TNF inhibitor or other equivalent FDA approved treatment. The direct effect on the myocardial function, structure, LV mass, and subendocardial hypoperfusion will be evaluated over 6 months of observation. In this aim as already noted above - we will utilize only FDA approved drugs for RA, and the study will be conducted and monitored in the context of usual care.

## 2. STUDY DESIGN AND STATISTICAL PROCEDURES

### 2a. Study Design

(this section includes references)

For aim 1, the proposed studies will be performed in 150 patients with RA and 15 subjects without RA who will function as controls. The 150 patients will be recruited from the rheumatology clinics at New York Presbyterian Hospital of the Columbia University. The 15 control subjects will be recruited from the internal medicine clinics at the same institution or among friends of the recruited RA patients.

The 150 participants should have RA fulfilling established diagnosed criteria and not have a history of cardiovascular disease as indicated in the section for inclusion/exclusion criteria

[figure not shown]
These patients (150) will undergo the evaluations shown in the table below - and in more detail in Appendices I, II and III - during an initial visit (Visit I).

Evaluations	Visit I September/2011 - August/ 2014
Cardiac PET-CT scan*	X
3D Echocardiogram & CV Questionnaires	X RA X
Joint examination	X
Phlebotomy	X
Anthropometry	X
DEXA scan (body composition)**	X

\*including 3 transverse CT slices (mid-chest, L4-L5, mid-thigh) and cardiac CT for evaluation of coronary artery calcification (CAC).

\*\*only for the 50 participants who will be recruited for aim 2. (see below)

During the first PET scan a cardiac CT scan will be obtained in order to quantify coronary artery calcium (Agatston Score). Three additional CT Slices will be obtained (mid chest, lumbar, and mid thigh) to evaluate for visceral fat

accumulation as a risk factor for cardiovascular disease.

Controls will undergo only the PET-CT scan, 3D Echo, anthropometry evaluations, phlebotomy, and will complete abbreviated cardiovascular related questionnaires as outlined in Appendices I, II and III.

The PET-CT scan will occur on the same day or within one week of Study visit I.

We expect that the vast majority of the 150 enrolled patients will already be on treatment with methotrexate at the time of enrollment. Methotrexate is the cornerstone of treatment for RA and almost all patients are started on methotrexate upon diagnosis of RA as part of standard of care. However only approximately 50% of patients reach a state of RA remission or low disease activity with methotrexate. The other 50% of patients with RA do not respond adequately to methotrexate and need treatment with additional agents in order to reach remission or low disease activity. In usual care patients who do not respond to methotrexate are frequently prescribed medications such as sulfasalazine and plaquenil in addition to methotrexate (triple therapy) or a TNF inhibitor in addition to methotrexate. Whether a patient receives one (TNF inhibitor) or the other (triple therapy) treatment is a matter of physician and patient preferences most of the time. Published guidelines provide only initial treatment recommendations (for example: methotrexate for all RA patients once diagnosis is established) and do not comment on whether one therapeutic agent should be preferred over an other for patients who do not respond to methotrexate (1).

For aim 2, we will identify 50 of the patients enrolled in aim 1 who are in need for further treatment due to increased RA activity despite methotrexate treatment. These patients will be recruited to continue in the study for an additional 24 (+/- 2) weeks (6 months). The patients will be randomized to receive one of the FDA approved options in an open label protocol for increased disease activity; either a TNF inhibitor or triple therapy and in the context of standard of care as already noted above. For more information regarding inclusion/exclusion criteria please refer to the appropriate IRB/RASCAL application section below.

Although treatment with TNF inhibitor and methotrexate is slightly superior in slowing radiographic joint damage, triple therapy has comparable efficacy and multiple clinical trials (COBRA and Best) robustly support the ability of the regimen to effectively reduce disease activity and slow radiographic damage (2,3).

After the escalation in their treatment at baseline (Study Visit I) these patients will return for a second (24 weeks) study visit respectively and the set of evaluations shown in the table below - and in more detail in Appendices I, II and III - will take place. A window of +/- 2 weeks will be allowed in scheduling the study visits.

Visit II	
Evaluations	Mar/2012-Jan/2015
Cardiac PET-CT scan*	X
3D Echocardiogram	X RA &
CV Questionnaires	X
Joint examination	X
DEXA scan (body composition)	X
Phlebotomy	X
Anthropometry	X

\*including 3 transverse CT slices (mid-chest, L4-L5, mid-thigh) and low dose radiation chest CT

During PET-CT scans a low dose CT imaging of the chest is always obtained for attenuation correction as part of the usual PET-CT protocol. Although we will not need a repeat coronary artery calcium score at visit 2, low dose radiation CT imaging of the chest is always obtained for attenuation correction as part of the usual PET protocol. During this CT imaging acquisition 3 additional slices (CT cuts) will be again obtained (mid chest, lumbar, and mid thigh) to evaluate for change in visceral fat following treatment initiation.

The 3-dimensional Echocardiogram (3D Echo) will be performed to provide a measure of LV mass and will be performed in every study visit.

The 15 controls will also be asked to have a repeat set of evaluations 6 months (24 +/- 2 weeks) after their first evaluation without any therapeutic or other intervention in between the two visits. The inclusion of non-RA controls will provide important data on the normal variation of cardiac PET-CT and 3D Echo parameters over time. Further evaluations for the control participant visits are outlined in appendices I, II and III.

Every subject (RA patient or non RA control) will have a urine pregnancy test prior to tests involving radiation exposure (PET-CT scan and DEXA) and on the same day.

The screening and consent process of a patient to receive randomized escalation of treatment will be made at the time they are consented for the first study visit. It is possible that all 150 patients will qualify for randomization of their treatment but only the first 50 of those will be selected to return for study visit II. The rest of the patients will exit the study and will continue their regular care with escalation of their treatment by their treating rheumatologist outside the study.

Standard of care entails that patients who undergo escalation of their treatment need to be evaluated every 6-8 weeks to evaluate response to treatment, the need for further treatment escalation, and toxicity monitoring. Thus in between Study Visits I and II patients will return every 6-8 weeks for safety visits which will mirror standard of care management and which will be focused on toxicity monitoring as it would happen even if the patients did not participate in the study. An exit safety visit will occur 6-8 weeks after visit II. The incorporation of safety visits in the study and the related procedures/tests are shown in Appendices I and II.

It is possible that patients randomized to receive either the triple therapy or treatment with a TNF inhibitor and methotrexate may not respond to treatment. Disease activity will be evaluated using the Clinical Disease Activity Index (CDAI) score at the time of every safety and study visit and treatment will be modified until they reach the state of low disease activity or remission as defined by a CDAI score of less than or equal to 10. CDAI score takes into account the number of swollen and tender joints and the evaluation (using a Visual Analog Scale) of disease activity by both the patient and the physician. CDAI is an extensively validated disease activity tool.

[figure not shown]
The treatment algorithm followed in this study is described below. A study flow chart describing the algorithm is provided in appendix XXI.

i. Randomization to the non TNF inhibitor arm: Patients on triple therapy will be started on 1 gram of sulfasalazine (SSZ) twice daily along with weight adjusted daily Hydroxychloroquine (Plaquenil). Methotrexate treatment will be continued. It takes approximately 6 weeks before an effect of this therapeutic regimen is experienced. In the first safety visit (which will happen approximately 8 weeks after the first study visit) the need to increase the SSZ to 3 grams daily will be evaluated based on whether the patient has reached low disease activity status or remission. In the subsequent safety visit (safety Visit 2) which will occur 8 week after Safety Visit 1, if disease activity remains moderate or high, SSZ and Hydroxychloroquine will be stopped and patients will be switched to Leflunomide (Arava) 10 mg plus methotrexate.

Patients will then return at 24 weeks for their second Study Visit (Study Visit 2) for completion of the study and further management as per standard of care.

An additional Safety Visit (Safety Visit 3) will take place at 32 weeks and will serve as an exit safety visit.

ii. Randomization to the TNF inhibitor arm: For patients randomized to receive treatment with a TNF inhibitor, disease activity will also be evaluated at the time of every visit. The effect of TNF inhibitors on arthritis activity may be observed as early as in 2 weeks but sometimes may take up to 14 weeks (approx. 3 months). At the time of the first safety visit tolerability and safety will be evaluated. At the time of Safety Visit II if CDAI is still >10 (indicative of moderate disease activity) an increase in the dose or frequency of the TNF inhibitor (in the case of agents such as infliximab or adalimumab where escalation of dosage is an option) or a switch to treatment to an alternative TNF

inhibitor will take place.

Patients will then return at 24 weeks for their Second Study Visit (Study Visit 2) for completion of the study and further management as per standard of care.

An additional Safety Visit (Safety Visit 3) will take place at 32 weeks and will serve as an exit safety visit.

The treatment algorithm described above is similar to the care patients would receive even if they did not participate in the study. The only difference is that patients will be randomized to receive one of the two standard of care treatments. The need for prednisone to temporarily control disease activity will be decided by the investigators according to usual standards of care.

As already mentioned decisions to escalate treatment will be based on CDAI score which is a composite disease activity score consisting of counts of swollen and tender joint counts and evaluation of disease activity by both the patient and the physician using a visual analog scale. The joint counts will be performed by a blinded trained joint assessor. Either a faculty member or a senior rheumatology fellow, also not aware of the patient treatment will perform the joint examinations and the assessment of disease activity. The same joint assessor will perform the joint counts for a given patient throughout the study. Every time CDAI is  $>10$ , then a change in the treatment according to the algorithm described above will be mandated to ensure patients' well being.

[figure not shown]
As already mentioned, the goal of this study is to investigate the "low LV mass phenotype" in patients with RA and its contributors in an attempt to elucidate the pathophysiology pathways that may connect RA with alterations in the myocardium and the evolution to heart failure. 3D-Echo will be used to measure the LV mass. Cardiac PET-CT imaging will be used to evaluate myocardial function (cardiac output, ejection fraction), microvasculature function (myocardial perfusion) and myocardial inflammation (F18-FDG uptake).

The research questions to be addressed with the study visit I are the following:

- i) Are anti-CCP antibodies or other RA-specific characteristics (e.g., disease duration, activity, severity) associated with lower LV mass (or other LV parameters of structure/function)?
- ii) What is the prevalence, the degree and correlates of microvascular dysfunction in RA? Is it associated with low LV mass or reduced global or regional contractility? Is it associated with systemic, articular and/or myocardial inflammation?
- iii) What are the prevalence, patterns, distribution and severity of inflammation as measured by F18-FDG uptake in myocardial PET imaging? Are intensity and/or distribution of F18-FDG uptake correlated with low LV mass or global or regional contractility? Does the severity/distribution of F18-FDG uptake correlate with levels of systemic and/or articular inflammation?

For the second aim of this study the goal is to evaluate the effect of TNF inhibitors on the myocardium. For the 50 patients undergoing randomization and the controls the questions to be addressed will be the following:

- i) Are global measures of LV structure (e.g., mass) or contractility (e.g., ejection fraction) affected (reduced or increased) by treatment with TNF antagonists? Is there a different effect compared to alternative therapy?
- ii) If microvascular dysfunction and/or inflammation are present before treatment, do they improve with treatment with TNF compared to alternative treatment? If parameters improve only with TNF inhibitor, this would suggest that TNF inhibitors exert a local anti-inflammatory effect on the myocardium mechanistically different compared to alternative treatment.
- iii) If treatment-induced improvements in microvascular dysfunction and/or inflammation (F18-FDG uptake) are

observed with TNF inhibitor treatment and not with alternative treatment, do they correlate with (or mediate) global (or regional) changes in LV structure or function? If so, this would suggest a causal relationship between regional myocardial vasculopathy and/or inflammation with LV dysfunction.

iv) Do treatment-induced improvements in systemic inflammation (e.g., CRP) and RA disease activity correlate with changes in myocardial microvascular perfusion and/or inflammation? If so, this would suggest a relationship between systemic and myocardial inflammation.

In preliminary exploratory data analyses, summary statistics for the continuous and categorical variables will be calculated, including means, standard deviations, quartiles and ranges, and for the categorical variables, counts and percentages. In initial analyses, statistical comparison of continuous variables will be conducted using the t-test or nonparametric method, as appropriate. The comparisons of the prevalence of categorical CV risk factors will be conducted using the Chi-square test or the Fisher's exact test, as appropriate. All comparisons will be conducted at the  $\alpha=0.05$  level of significance using two-tailed tests, unless otherwise noted. To account for the potential for multiple comparisons artifact: a) First, significance testing will be based on a priori hypotheses and not spurious significant p-values; b) Second, if multiple comparisons are undertaken, adjustments in the threshold for statistical significance will be made as necessary. If multiple and collinear variables are detected, appropriate techniques will be utilized to minimize the impact of collinearity on the statistical efficiency of the derived parameter estimates.

To explore the associations of anti-CCP antibody, which can be analyzed as a dichotomous or continuous variable, other characteristics of RA (e.g. duration; activity; severity), and myocardial FDG uptake with continuous measures of global LV structure (e.g. LV mass) and function (e.g. ejection fraction, end-systolic volume stroke volume), we will perform descriptive analyses and potential data transformation as needed required to meet the requirement for statistical tests involved. LV structural and functional outcomes for those with presence/absence of anti-CCP antibody, longer/shorter RA duration, or more/less severe RA will be compared using t-tests or an appropriate non-parametric test. Association between LV structural and functional outcomes and anti-CCP antibody level and other RA characteristics as continuous predictors will be examined using nonparametric approach such as Loess plots to explore the natural form of the associations. Multivariate regression models (linear, polynomial, or piecewise regression, as appropriate) will be used to evaluate whether associations are independent of potential confounders. This will include explicitly adjusting for conventional CV risk factors in the investigation of associations of LV mass/contractility with RA characteristics to studying the degree in which these associations are independent of these risk factors.

Linear mixed effects (MIXED) regression models will be used to assess trends in LV structure and functional outcomes over time between the two visits for the patients who will undergo randomization reevaluation with PET-CT and 3D Echocardiogram, while controlling for potential confounders. The data will include PET-CT studies for 25 RA patients receiving TNF antagonists and 25 RA patients receiving alternative treatment, and PET-CT studies for 15 non-RA patients. The data are longitudinal since LV outcomes are measured for each person at 2 different time points. Since repeated measures tend to be correlated within a person, mixed models with both fixed and random effects will be used to adjust for this correlation. We will use unstructured correlation structure given that each visit will occur roughly around a fixed time since study visit I, and use robust standard error estimates to conduct statistical inferences. To study the TNF inhibitor effects on LV structure or functional outcomes, visit-specific indicators, RA status, TNF treatment status, and visit x TNF treatment interaction will form the bases for the mean model. The visit-specific indicators will capture the time trend of LV outcomes over the study period, the RA status will delineate the overall mean difference in LV outcomes between RA and non-RA, with the TNF treatment status indicator and its interaction with visit indicators capturing the baseline difference in LV outcomes between TNF treated and non-treated groups and the potential TNF treatment effect on LV outcome over time, respectively. Actual TNF inhibitor dosage could be used in place of TNF status indicator in the model if necessary, and other potential covariates could be added into the model for confounding adjustment. For example, inflammation markers could be added into the model to examine whether any TNF treatment effect is mediated through the change in systemic inflammation. Similar modeling approaches can be used to study all research questions of interest using the corresponding outcomes and their hypothesized predictors listed in those questions to be addressed. For any binary outcomes in this type of regression analysis, e.g. indicator of whether a LV outcome exceeding certain critical value, generalized linear mixed effects models (GLIMMIX) can be used to study the odds of such outcome as a function of the independent variables.

All analyses will be performed with STATA statistical software, version 9.0 (STATA Corp, College Station, TX) and PLINK (<http://pngu.mgh.harvard.edu/~purcell/plink>). In all tests, a two-tailed alpha error of 0.05 will be defined as the level of statistical significance.

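### The visit-by-TNF term in the aim 2 mixed model compares TNF inhibitor with triple therapy and untreated controls pooled, and the TNF-only inference is not tied to a TNF-minus-triple estimate

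*Combined protocol and SAP*

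**What the plan says.** Section 2a (Study Design) lists the aim 2 questions. Question ii asks of microvascular dysfunction and inflammation, "do they improve with treatment with TNF compared to alternative treatment". It then gives the reading of a positive result: "If parameters improve only with TNF inhibitor, this would suggest that TNF inhibitors exert a local anti-inflammatory effect on the myocardium", by a mechanism different from that of the alternative treatment. Question iii, on whether these improvements correlate with or mediate LV changes, is posed for improvements "observed with TNF inhibitor treatment and not with alternative treatment".

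The mixed model later in section 2a is fitted to 25 TNF, 25 alternative-treatment and 15 non-RA participants. Visit indicators, RA status, TNF status and "visit x TNF treatment interaction will form the bases for the mean model". On RA status the text says: "the RA status will delineate the overall mean difference in LV outcomes between RA and non-RA". The visit-by-TNF term is presented as the potential TNF effect over time. Of the other questions, the section says: "Similar modeling approaches can be used to study all research questions of interest".

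Controls are re-examined at 24 weeks "without any therapeutic or other intervention in between the two visits". Section 2b states power for TNF versus triple therapy on LV mass (more than 85% for 27 g) and on FDG uptake (more than 80% for a 50% decrease).

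**The concern.** A claim that TNF inhibitors act on the myocardium differently from triple therapy rests on one quantity: the change under TNF minus the change under triple therapy in randomised patients. Two parts of section 2a do not deliver it.

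**The model term.** RA status enters as a constant shift, so the only time trends allowed are one for TNF patients and one for everybody else. The comparator for TNF is then a mixture of treated RA patients and untreated people without RA. A benefit common to both RA arms appears in part as a TNF effect.

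**The wording of questions ii and iii.** The inference and the entry to question iii turn on improvement in one arm and its absence in the other. No criterion is given for either, and neither is linked to the between-arm comparison that question ii itself asks for.

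A shared benefit is a realistic case. Section 2a says that "triple therapy has comparable efficacy and multiple clinical trials (COBRA and Best) robustly support the ability of the regimen to effectively reduce disease activity", and both arms are treated to low disease activity. Those statements concern joints; whether the myocardium follows is question iv.

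**Working it through.** **1. The plan's own figures.** LV mass, TNF versus triple: SD 27 g and correlation 0.35 (section 2b) give SD of change = 27 × √(2 × (1 − 0.35)) = 30.8 g. A two-sided 0.05 t-test with 25 per arm has 86.0% power for 27 g, so the stated figure of more than 85% reproduces without drop-out. Stroke volume (SV), within the TNF arm: SD 4.2 and correlation 0.2 give SD of change = 4.2 × √(2 × (1 − 0.2)) = 5.313 mL/m2. Power for a change of 3.42 is 80.1% at n = 21 and 82.1% at n = 22, in line with the stated 80%.

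**2. What visit-by-TNF estimates.** The mean model implies:

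| Group | Visit I | Change to Visit II |
|---|---|---|
| Control | b0 | bV |
| Triple | b0 + bRA | bV |
| TNF | b0 + bRA + bTNF | bV + bV×TNF |

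Baseline means are free in all three groups, but control and triple share the change bV. With complete pairs and an unstructured covariance, bV is estimated by the pooled mean change of those two groups. Hence

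visit-by-TNF = TNF change − (n_triple × triple change + n_control × control change) / (n_triple + n_control).

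At 25/25/15 this is TNF − (0.625 × triple + 0.375 × control). Fitted models confirmed the identity. In one simulated data set the term was 2.793 while TNF minus triple was 1.328. In another, adding visit-by-RA-status made the term equal TNF minus triple.

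**3. Expected value under equal benefit.** Let both RA arms change by d and controls by 0. The term's expectation is d × n_control / (n_triple + n_control), where 0 is wanted. With 15% drop-out, taken as 21-22 per RA arm and 12-13 controls:

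- Share: 12/33 = 0.364 to 13/34 = 0.382
- d = 3.42: 3.42 × 12/33 = 1.24 to 3.42 × 13/34 = 1.31 mL/m2
- d = 5.2: 5.2 × 12/33 = 1.89 to 5.2 × 13/34 = 1.99 mL/m2

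**4. How often the term is significant in favour of TNF** (simulation, SV inputs as above, two-sided 0.05):

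| Shared change | Model-based SE | Robust SE (as planned) | TNF minus triple, RA only |
|---|---|---|---|
| 3.42 | 12-13% | 14-15% | 2.5% |
| 5.2 | 20-22% | 24-26% | 2.5% |

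**5. When there is no bias.** If triple and control changes are equal, the pooled comparator equals the triple arm in expectation. This is so in the SV scenario of section 2b (5.2 for TNF, 0 for the other two groups).

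**6. The TNF-only wording.** Assume, since the plan does not say, that it were judged by separate within-arm tests. With the same true change in both arms and power p in each, a false TNF-only result has probability p(1 − p). For SV at n = 21/22 this is 11% at a change of 1.0, 25% at 2.3 (the maximum), 15-16% at 3.42 and about 1% at 5.2.

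**The case against.** The strongest reply is that the comparison is already in the plan. Question ii is comparative, question i asks about a different effect from alternative therapy, the model is joint with a treatment interaction, and section 2b powers TNF against triple therapy for LV mass and FDG. The quoted sentence says only what a pattern would suggest; it is not a decision rule. This stands. A reader might infer that the plan has no between-arm comparison, or that it tests each arm separately, and the documents support neither. A within-TNF calculation is given, but no within-triple test is planned, so the figures in step 6 are conditional.

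A second reply is that SV is an LV function measure belonging to question i, whereas questions ii and iii concern perfusion and FDG uptake. This also stands. The documents give no SD or correlation for FDG or flow reserve, and the extension of the model to those outcomes is permissive. The rates in step 4 therefore do not size the error for question ii.

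A third is that the listed terms are a basis to which covariates may be added. The section offers covariates for confounding and for mediation by systemic inflammation; it does not name visit-by-RA-status.

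Finally, a reader might infer that all mediation work is closed when both arms improve. That goes too far: question iv and the systemic inflammation analysis carry no such condition. Only question iii does, and limiting it to a TNF-specific response could be a deliberate scientific choice.

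**Conclusion.** The model defect holds and needs no interpretation of the word only. As written, visit-by-TNF is TNF minus a pooled triple-plus-control comparator. When both RA arms benefit equally and controls are unchanged, it attributes 36-38% of the shared benefit to TNF. The false-positive rates for SV assume normal data, the SD and correlation of section 2b, and 15% drop-out. The bias depends on triple and control changes differing and on controls staying in the fit, as section 2a says they do.

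The wording of questions ii and iii is a lesser gap: the inference and the entry condition are not linked to the contrast that question ii asks for. The 25% maximum applies only if separate within-arm tests were used. Together these merit correction before analysis. They do not show that the plan lacks a between-arm comparison.

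**What to change.** **Mixed model, section 2a.** Add a visit-by-RA-status term, or estimate the treatment contrast in the randomised RA patients only. Either makes the term equal TNF minus triple. Controls can still describe normal variation over time.

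**Questions ii and iii, section 2a.** State that a conclusion of a different TNF effect is based on the TNF-minus-triple estimate and its 95% CI. Report each arm's change with its CI, and state that a non-significant change in the triple arm is not read as no effect. Report question iii alongside that estimate, without requiring absence of improvement in the triple arm.

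**Cost.** Some text and one model term; no new data. Precision falls somewhat. For SV with 21/21/12, the SE is 5.313 × √(1/21 + 1/21) = 1.64 for TNF minus triple, against 5.313 × √(1/21 + 1/33) = 1.48 with the pooled comparator. For 3.42 versus 0, the between-arm test on change has 53-55% power, against 80-82% for a within-arm test.
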